**Advancing Symptom Alleviation With Palliative Treatment (ADAPT)**  
**NCT02713347**  
**IIR 14-346**

**November 15, 2021**

**ADAPT Data Analysis Plan:**

Data from all participants will be included regardless of level of participation using an intent-to-treat approach. The primary outcome measure, FACT-G, will be analyzed as a continuous variable, while the secondary outcomes will be either continuous (disease-specific health status, depression, symptom burden, emergency department visits, hospitalizations) or binary (advance care planning communication and documentation; mortality).. Analysis models will adjust for the disease stratification variable used in randomization. Analyses of the repeated measures, including primary and secondary endpoints, will be performed with SAS 9.4 using maximum likelihood estimation (MLE) for incomplete data using linear mixed models for continuous outcomes and generalized linear mixed models with a logit link for binary endpoints. This approach has several advantages: 1) all available data on eligible subjects can be included in the analysis even when there are missing data at follow-up, 2) MLE estimates the correlation between related measures and adjusts test statistics appropriately, 3) time-varying covariates can be incorporated into the model, if desired, and 4) the assumptions about missing data are relaxed from missing completely at random to missing at random (Little RJ. Methods for handling missing values in clinical trials. *J Rheumatol* 1999;26(8):1654-1656). The primary analyses will not consider the pre-randomization variables, but the effect of these variables on outcomes will be investigated as secondary analyses.

The primary outcome will be the difference between intervention and control in the change in FACT-G from baseline to 6 months. To describe the treatment by disease interaction, we will estimate the treatment effect and its confidence interval within each of the disease groups. Missing data will be reviewed to identify potential patterns and examined to assess how these patterns impact our results. Specifically, we will examine plots of group means over time stratified by the time of the last completed observation to determine if biases are evident due to missing data (Fairclough DL. Design and analysis of quality of life studies in clinical trials. CRC press; 2nd Edn, 2010). When data are missing at random, unbiased results can still be obtained from the likelihood method used in the analysis. If we find evidence of data missing not at random, sensitivity analyses will be performed using pattern mixture models (Little RJ, Wang Y. Pattern-mixture models for multivariate incomplete data with covariates. *Biometrics* 1996;52(1):98-111) and results will be presented to assess the impact of missing data on the reported conclusions.

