12. Demographics/Study Form: Age, gender, race and ethnicity, education level, and clinical variables will be determined at the enrollment visit from the electronic medical record and patient self-report. For example, spirometry results (COPD), NYHA classification (CHF), etiology of CHF or COPD, most recent ejection fraction (CHF), and BNP or NT-pro BNP (CHF) will be documented. Medical history (including comorbidities), current medications, number of hospitalizations in the previous year will also be collected at the time of the enrollment visit. Patients' current care, including palliative care, mental health, cardiology, pulmonology, hospice and specialist pain care will be ascertained at baseline and 6 months. At the 6 and 12 month study visit, patients will be asked to relate interim events, including hospitalizations, the reasons for them, and for permission to obtain medical records relevant to such events from VA and non-VA facilities. Medications from the medical record will be documented again at the six month visit.

13. Advance care planning communication will be measured using patient report questions at the baseline and 6 month study visits. Advance directive documentation will be defined by the presence of any of the following notes in the electronic medical record at baseline and 6 months: advance directive discussion; scanned advance directive (either a living will or durable power of attorney for health care); or medical orders for life-sustaining treatment.

14. Hospitalizations/emergency room visits, mortality and risk of hospitalization and/or death: The following events will be assessed during the study period through VA and non-VA facility medical record review to supplement patient report: hospitalization (with cause) and mortality. We will also review medical records for intensive care use and end of life care patterns. We will also assess risk of hospitalization and/or death for participants during the study. Vital status will also be ascertained via the VA Vital Status File and the National Death Index.

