## **F. Data Analysis Plan:**

### **Aim 1 Data Analysis**

*Descriptive Statistics and Basic Comparisons.* All analysis variables, including predictors, covariates, and outcomes, will be examined carefully prior to any formal statistical analysis. Standard graphical methods, including histograms and boxplots, will be used to examine overall distributions and identify potential outliers, which will be confirmed prior to inclusion in analysis. Internal consistency of multi-item scales will be examined using Cronbach's alpha, and whenever possible, items and scales will be compared to existing findings on their psychometric properties to ensure appropriate performance. Data transformations will be considered, such as log transformations for highly skewed data, to meet model assumptions. Each measure will be summarized using standard descriptive statistics, including means and standard deviations, medians, and ranges for continuous measures and proportions for categorical measures. Baseline characteristics will be compared between groups using appropriate tests, such as Chi-square and t-tests.

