*Primary/Secondary Analyses.* Data from all participants will be included regardless of level of participation using an intent-to-treat approach. The primary outcome measure, FACT-G, will be analyzed as a continuous variable, while the secondary outcomes will be either continuous (disease-specific health status, depression, symptom burden, emergency department visits, hospitalizations) or binary (advance care planning communication and documentation; mortality). Due to the short follow-up period, time-to-event analyses will not be used. Analyses of the repeated measures, including primary and secondary endpoints, will be performed with SAS 9.4 using maximum likelihood estimation (MLE) for incomplete data using linear mixed models for continuous outcomes and generalized linear mixed models with a logit link for binary endpoints. This approach has several advantages: 1) all available data on eligible subjects can be included in the analysis even when there are missing data at follow-up, 2) MLE estimates the correlation between related measures and adjusts test statistics appropriately, 3) time-varying covariates can be incorporated into the model, if desired, and 4) the assumptions about missing data are relaxed from missing completely at random to missing at random. The primary analyses will not consider the pre-randomization variables, but the effect of these variables on outcomes will be investigated as secondary analyses. We will add a random intercept for PCP to the analytic models to account for clustering of outcomes by practice patterns.

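### Hospitalizations and emergency visits, which are event counts, go into linear mixed models with no time at risk, no rule for death, and no use of the prior-year hospitalization count in the main models

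*SAP*

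**What the plan says.** **Scale and model.** The SAP's single analysis section states that "the secondary outcomes will be either continuous (disease-specific health status, depression, symptom burden, emergency department visits, hospitalizations". The same list stands in the protocol (section F, Aim 1 Data Analysis, Primary/Secondary Analyses). Both documents name only two model families. In the SAP the analysis is done "using linear mixed models for continuous outcomes and generalized linear mixed models with a logit link for binary endpoints", and the protocol has matching text. No count model, offset or exposure term appears in either. The protocol also rules out time-to-event methods because follow-up is short. The SAP drops that sentence but puts no time-at-risk method in its place.

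**Covariates.** The SAP says: "Analysis models will adjust for the disease stratification variable used in randomization". It adds: "The primary analyses will not consider the pre-randomization variables, but the effect of these variables on outcomes will be investigated as secondary analyses".

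**Data available.** Under the protocol's Outcome Measures, the demographics item says that "number of hospitalizations in the previous year will also be collected at the time of the enrollment visit". No prior-year count of emergency visits is listed. The item on hospitalizations, emergency visits and mortality says that events are ascertained "through VA and non-VA facility medical record review to supplement patient report", with vital status from the VA Vital Status File and the National Death Index. Table 5 marks utilization at months 6 and 12 only, so the prior-year count is the only listed baseline measure of utilization.

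**Transformation.** The protocol's descriptive-statistics paragraph says transformations will be considered, "such as log transformations for highly skewed data, to meet model assumptions". It does not tie this to utilization, and the SAP does not repeat it.

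**The concern.** Emergency visits and hospitalizations are named secondary outcomes in Aim 1. They are event counts: many patients will have none, a few will have several, and the variance grows with the mean. A normal-theory linear model describes such data poorly, and its estimate is not expressed per unit of time.

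For CHF and COPD the trial enrolls patients chosen for high risk of hospitalization and death, and the Sample Size section expects 5% to die. Some follow-up will therefore be cut short, and the plan does not say what happens then. If the shortened count is entered as complete, an early death looks like low use. If the interval after death is left to the likelihood for incomplete data, the model in effect imputes admissions after death. These are different estimands, and the choice should be made before the data are seen. Mortality is itself an Aim 1 outcome, so equal death rates in the two arms cannot be assumed.

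For FACT-G, the protocol adds the baseline value to gain precision. For hospitalizations a comparable baseline is collected, but no model names it.

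**Working it through.** **1. The plan's own power figure.** The only powered comparison is FACT-G: 115 per arm, effect size 0.4, two-sided 0.05. By the normal approximation, 0.4 × √(115/2) = 3.03; 3.03 − 1.96 = 1.07; Φ(1.07) = 0.858, against 85% stated. No event rate, sample size or power is given for utilization, so steps 2 and 4 rest on assumed rates.

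**2. What the prior-year count is worth.** Assume each patient has a personal rate with mean λ per year, overdispersion k, and a follow-up of t years. With m₁ = λ and m₂ = λt, each count has variance m + k·m², and the covariance of the two counts is k·m₁·m₂. Hence r = k·m₁·m₂ / √[(m₁ + k·m₁²)(m₂ + k·m₂²)], and adjustment is worth about r² of the sample size.

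- Low end (λ = 0.5, k = 0.5, t = 0.5): r = 0.0625 / √(0.625 × 0.28125) = 0.15, so r² ≈ 2%.
- High end (λ = 1.2, k = 2, t = 1): r = 2.88 / 4.08 = 0.71, so r² ≈ 50%.
- If patient risk drifts so that r is halved (0.07 to 0.35), adjustment is worth 1% to 12%.

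**3. Bias from ignoring time at risk.** If deaths are spread evenly over the period, a death fraction d loses d/2 of the person-time. With no true effect, the apparent rate ratio (intervention/control) is (1 − d_int/2)/(1 − d_ctl/2).

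| Deaths, control vs intervention | Apparent rate ratio |
|---|---|
| 5% vs 5% | 1.000 |
| 5% vs 2% | 0.990/0.975 = 1.015 |
| 8% vs 3% | 0.985/0.960 = 1.026 |
| 10% vs 5% | 0.975/0.950 = 1.026 |

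**4. Simulated power and type I error.** Two sample sizes were used: 150 per arm (400 less 25%, halved) and 200 per arm (record review reaches everyone). Both assume 5% deaths.

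*150 per arm, 800 replicates per cell, 6 months, rate ratio 0.65, fully stable risk. Count model: robust Poisson with offset and log prior count.*

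| Mean events per 6 months | Gamma shape | Linear, unadjusted | Count model | Gain (points) |
|---|---|---|---|---|
| 0.3 | 0.5 | 32% | 39% | 7 |
| 0.3 | 1.0 | 35% | 39% | 4 |
| 0.6 | 0.5 | 45% | 60% | 15 |
| 0.6 | 1.0 | 56% | 64% | 8 |
| 1.0 | 0.5 | 53% | 81% | 28 |
| 1.0 | 1.0 | 68% | 81% | 13 |

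About 50-80% of patients have no event. Null rejection is 3.4-7.1% (linear) and 4.9-6.2% (count model). The link and offset alone add 0-2 points.

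*200 per arm, 400 replicates per scenario. Count model: negative binomial with offset and log prior count.*

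- 0.8 events per year, overdispersion 1-2, 6 months, rate ratio 0.6: linear 56-70%, count model 62-72%, a gain of about 1-9 points.
- 1.2 per year, overdispersion 2, stable risk, 12 months: 55% against 71% at rate ratio 0.7, and 84% against 94% at 0.6.
- In the rate-ratio 0.7 case, adding the prior count to the linear model alone moves power from 55% to 67%.
- Null rejection of the unadjusted linear model is 5.0-6.5%. Negative binomial with offset and no prior count gains 0-7 points over it, but in some scenarios rejected in 7-7.5% of null runs. The Monte Carlo standard error at 5% is 1.1 points.

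**The case against.** The strongest reply is that little is broken. In a randomized comparison of this size the linear model gives a valid difference in mean events per patient, with type I error near 5%. The link and offset alone add little power. Difference or ratio is largely a choice of estimand. All of this stands, so a reader who infers that the linear analysis is invalid goes too far.

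Three other inferences are tempting and are not supported:

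- *That the plan scores early deaths as low use, or treats the time after death as missing at random.* Neither document says how death is handled for these outcomes. The defect is silence, and at about 5% deaths the resulting bias is small.
- *That the prior-year count is discarded.* Both documents leave pre-randomization variables to secondary analyses. The count is deferred, although no model for utilization is given there.
- *That utilization was a stated priority of the operational partners.* The protocol's rationale for Aim 2 says they cared most about personnel time and costs, together with quality of life and advance care planning.

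It is also fair to say that the larger power gains assume stable patient risk, that the covariate has no like-for-like version for emergency visits, and that an offset for days alive does not remove the problem of death but targets a rate while alive. The log transformation is offered only as an example, and adding a constant would deal with zeros, but nothing in the plan applies it here.

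What the reply does not answer is that the estimand under death is undefined and a collected predictor is missing from the main models.

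**Conclusion.** The point holds as a matter of specification and efficiency, not validity. Two skewed event counts are modelled as continuous, with no time at risk, no rule for death and no main-model use of the prior-year hospitalization count.

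The cost in power for hospitalizations runs from about 1 point to roughly 15 points, and up to 28 in the most favourable cell (mean 1.0 per 6 months, strong heterogeneity, fully stable risk). Most of it comes from the omitted covariate. The range rests on assumed event rates, overdispersion and stability of risk. For emergency visits the prior hospitalization count is only a proxy, so these gains do not carry over.

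Bias from ignoring time at risk is nil when deaths are equal, and at most a factor of 1.026 in the unequal cases shown. It could matter more in the longer-term utilization analyses the protocol plans, with records followed for up to ten years, because more deaths will accumulate. These are secondary outcomes, and the primary FACT-G conclusion does not depend on them.

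**What to change.** In the SAP's analysis section and the protocol's Primary/Secondary Analyses paragraph, take emergency department visits and hospitalizations off the continuous list and specify:

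- a count model with log link (Poisson with robust variance, or negative binomial), with log days alive and under observation as offset;
- adjustment for disease stratum and prior-year hospitalizations, for example log(count + 0.5), noting that for emergency visits this is a proxy;
- the rate ratio with its confidence interval, stated to be a rate while alive and reported beside mortality by arm;
- the difference in mean events per patient as a supplement.

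Given the null rejection rates above, robust Poisson is the safer default.

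The cost is a few sentences and a few lines of SAS. Record review, the vital status sources and the prior-year count are already planned. The downside is that the headline becomes a while-alive rate ratio, which is harder to explain than a mean difference and must be read together with mortality.

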Research staff at VA ECHCS will assist PSVAHCS in some aspects of recruitment, follow-up data collection and the process evaluation. The Intervention SW and RN at each site will interact with participants at both sites.

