#### Randomization - Aim 1:

Randomization will occur at the patient level with 1:1 randomization of patients to intervention or control groups. Randomization will be computer generated using random block sizes and stratified by site and disease CHF, ILD, or COPD, or both CHF and COPD.

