#### Sample Size

The sample size was planned to detect a clinically significant change on the primary outcome, quality of life. We plan to enroll 400 Veterans and anticipate 5% will die and 15-20% will have missing outcome data because they did not complete surveys or dropped out. Thus approximately 115 Veterans per arm will complete the study. With this sample size, we will have 85% power to detect a moderate effect size of 0.4 (two-sided test, alpha=0.05). The minimal clinically important difference on the FACT-G is 4-6 points, and with a standard deviation of 15, a Cohen's d effect size of 0.4 will be on the high end of clinical significance. We believe this is appropriate as this is a personnel-intensive intervention. **Table 3** illustrates a range of sample sizes per study arm with different power and effect size assumptions.

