The primary outcome will be the difference in FACT-G score at 6 months. Because of the anticipated high correlation of baseline FACT-G with follow-up FACT-G ( $r>0.5$ ), we will include the baseline FACT-G as a precision variable in the mixed model. To describe the treatment by disease interaction, we will estimate the treatment effect and its confidence interval within each of the disease groups (CHF, ILD, COPD) using disease-specific health status measures (KCCQ, K-BILD, CCQ) at the 6 month endpoint. In exploratory analyses, we will estimate treatment effect within illness subgroups (CHF, ILD, and COPD) on the primary outcome, and within subgroups of illness, including CHF (preserved vs. reduced ejection fraction) and COPD (defined by spirometry and imaging). Missing data will be reviewed to identify potential patterns and examined to assess how these patterns impact our results. Specifically, we will examine plots of group means over time stratified by the time of the last completed observation to determine if biases are evident due to missing data. When data are missing at random, unbiased results can still be obtained from the likelihood method used in the analysis. To account for the possibility of data missing not at random, sensitivity analyses will be performed using pattern mixture models and results will be presented to assess the impact of missing data on the reported conclusions. Among those who were hospitalized or died, we will examine for differences in

intensive care utilization and patterns of care at the end of life. We will also examine for intervention effect on longer term health care utilization (e.g., hospitalization, intensive care utilization).

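### Randomization is stratified by site and disease, but the SAP adjusts for disease only; adding site to the primary model is a small, free improvement

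*SAP*

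**What the plan says.** - **Allocation.** Protocol, Randomization - Aim 1: 1:1 at the patient level, in random blocks, "stratified by site and disease CHF, ILD, or COPD, or both CHF and COPD".
- **Model adjustment.** SAP, ADAPT Data Analysis Plan: "Analysis models will adjust for the disease stratification variable used in randomization". Site is named nowhere in the SAP.
- **Other baseline variables.** Same SAP section: "The primary analyses will not consider the pre-randomization variables". The sentence goes on to defer the effects of such variables to secondary analyses.
- **Endpoint.** The SAP defines it as "the difference between intervention and control in the change in FACT-G from baseline to 6 months". It does not say whether baseline FACT-G is a modelled response, part of a change score, or a covariate.
- **Protocol model.** Protocol, Aim 1 Data Analysis, also has no site term. It states that "we will include the baseline FACT-G as a precision variable in the mixed model" and adds a random intercept for the primary care provider (PCP), which the SAP does not repeat.

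**The concern.** The SAP adopts the principle that a factor used to stratify the allocation belongs in the model, applies it to one of the two factors, and gives no reason for leaving out the other. Stratified allocation balances the arms within each site, so the treatment difference is not affected by site variation. A model without site still counts that variation as noise. The reported standard error is then larger than it need be, and some of the precision bought by stratifying is not used.

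The SAP's wording also conflicts with itself. Disease is a pre-randomization variable, so the text adjusts for one such variable and then says that the primary analysis considers none.

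At stake is a little power for FACT-G and, in the logit models, a slight pull of the conditional odds ratio towards 1 if site is prognostic.

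**Working it through.** **Inputs from the protocol (Sample Size; Aim 1 Data Analysis).** Two-sided alpha 0.05; effect 0.4 SD, which is 6 points "with a standard deviation of 15"; 115 completers per arm; baseline to follow-up correlation above 0.5. The same section says to "anticipate 5% will die and 15-20% will have missing outcome data". That is 20-25% of 200 per arm, so 200 × 0.80 = 160 or 200 × 0.75 = 150 completers. Results are shown for 115, 150 and 160.

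**Assumptions.** Two equal sites; arms balanced within site among completers; equal SDs at baseline and 6 months; r = 0.5 (0.7 as a variant); a site difference in FACT-G change of D = 2, 3 or 5 points. The documents give no site difference.

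**Step 1: the plan's own figure.** Power = Φ(6/(15 × √(2/115)) − 1.960) = Φ(3.033 − 1.960) = 85.8%, against the stated 85%. It reproduces.

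**Step 2: change score, or baseline as a response.** Here only a site difference in change matters.
- SD of change: s = 15 × √(2(1 − r)) = 15.0 at r = 0.5.
- Inflation of residual variance without site: v = 1 + D²/(4s²). For D = 5: 1 + 25/900 = 1.0278.
- Actual alpha: 2Φ(−1.960√v).
- Power without site: Φ(6/(s√(2/n)) − 1.960√v). For D = 5, n = 115: Φ(3.033 − 1.987) = 85.2%.

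| D | v | Actual alpha | Loss (points), n = 115 | n = 150 | n = 160 |
|---|---|---|---|---|---|
| 2 | 1.0044 | 0.0495 | 0.10 | 0.06 | 0.05 |
| 3 | 1.0100 | 0.0489 | 0.22 | 0.13 | 0.11 |
| 5 | 1.0278 | 0.0469 | 0.62 | 0.36 | 0.30 |

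Power with site is 85.8%, 93.4% and 94.7%. At r = 0.7 (s = 11.6) the largest loss is 0.28 points at 115 and 0.08 at 150.

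**Step 3: baseline FACT-G as a covariate (the protocol's model).** A constant site difference in level, L, does not cancel here. With slope 0.5, about half of it stays in the residual.
- Residual variance with site: 225 × (1 − 0.25) = 168.75.
- Without site: a − c²/a, where a = 225 + L²/4 and c = 112.5 + L²/4.
- L = 5: 231.25 − 118.75²/231.25 = 170.27, ratio 1.009.
- L = 10: 250 − 137.5²/250 = 174.375, ratio 1.033.
- At 115 per arm, power is 93.85% with site, and 93.74% (L = 5) or 93.45% (L = 10) without: a loss of 0.11 or 0.40 points.

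**Step 4: a wider range.** Suppose instead that the total SD is 15 and site explains 1%, 5% or 10% of the variance at one time point (site differences of 3.0, 6.7 and 9.5 points). Actual alpha without site is 0.049, 0.044 and 0.039. At 115 per arm, adding site raises power from 86.0 to 86.2%, 86.5 to 87.5%, and 87.1 to 89.2%. A simulation with 20,000 replicates agrees: at 10%, type I error is 0.037 without site and 0.048 with it. If site has no effect, simulated power is 85.6% either way.

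**Step 5: does the model form matter for the fix?** Simulation with 800 runs per setting; totals of 230, 300 and 320; blocks of 4 or 6 within site and disease; an assumed 30/45/5/20% split over the disease strata; complete data at baseline and 6 months; disease already in the model. The ratio of the standard error with site to that without was:

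| Model | D = 3 | D = 5 |
|---|---|---|
| Baseline as response, site main effect only | 1.000 | 1.000 |
| Baseline as response, site and site-by-visit | 0.993 | 0.985 |
| Change score plus site | 0.995 | 0.986-0.987 |
| Follow-up adjusted for baseline, plus site | 0.993-0.994 | 0.982 |

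In the first row the estimate is identical too. If baseline is a response, a site main effect alone achieves nothing for the change contrast.

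**The case against.** The strongest reply is that this hardly matters. At the 150-160 completers per arm implied by the protocol's own attrition, Step 2 gives a loss of 0.05 to 0.36 points from a power of 93-95%, and the site differences behind it are assumed. The protocol also gives a reason to expect little site difference in delivery: "The Intervention SW and RN at each site will interact with participants at both sites". That is fair as to size, although each site has its own Team (Description of the Intervention), and a small gain is still worth taking when it is free.

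A second reply is that the SAP defers pre-randomization variables to secondary analyses, and site is one. This stands as far as it goes: site is not wholly ignored. It does not put site into the primary model.

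A third is that the protocol's PCP intercept would absorb part of a site difference if PCPs work within one site. That narrows the gap in the protocol, but the SAP does not contain the term.

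A reader might infer something stronger: that omitting a stratification factor biases the treatment effect or inflates the false-positive rate. The documents do not support this for FACT-G. Allocation is balanced within site by design, and the error runs towards caution. Nor should one infer that constant differences in level between sites never matter; Step 3 shows that they do when baseline is a covariate.

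**Conclusion.** The omission is real and its effect is small. Site is a stratification factor and is missing from the primary model. For the linear FACT-G model the consequence is a slightly conservative test: actual alpha 0.047 to 0.050, and about 0.1 to 0.6 points of power at 115 per arm, for site differences in change of 2 to 5 points with SD 15, r = 0.5 and equal SDs at both visits. The loss is smaller at 150-160 per arm. It reaches about 2 points only if site explains some 10% of the outcome variance, which nothing in the documents suggests. Equal SDs is itself an approximation, because entry requires FACT-G ≤ 70, which truncates the baseline distribution. The shift in the logit models' conditional odds ratio is a matter of direction only and was not sized. No conclusion about the trial's validity depends on this point.

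**What to change.** Replace the adjustment sentence with: *Models for the primary outcome will include both randomization stratification factors, site and disease, as fixed effects; if baseline FACT-G is a modelled response, site will also be interacted with visit.*

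Put this before "The primary analyses will not consider the pre-randomization variables": *Apart from the stratification factors, and baseline FACT-G where it serves as a precision variable.*

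Add site to the secondary models where the number of events allows. Mortality needs care: the protocol expects 5% of 400, about 20 deaths.

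The cost is SAP wording and one degree of freedom. A site-by-visit term over the four FACT-G visits (Protocol, Table 5) takes three more, against 230 completers on the protocol's figure or 300-320 on its attrition rates. Site is already recorded, because the allocation uses it.

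As a separate point, reconcile the PCP random intercept: carry it into the SAP, or state why it was removed.
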